Histone deacetylases (HDACs) have been implicated in the epigenetic regulation of innate and adaptive immunity. Increasing evidence supports the proposal that spectrum-selective inhibitors of class I HDACs can reverse immune evasion and elicit antitumor host response through immunostimulatory mechanisms. The immunomodulatory properties of class I HDAC inhibitors are reported to be mediated through multiple mechanisms including: 1) induction of programmed cell death ligand 1 (PD-L1) expression on the tumor cell surface, 2) induction of tumor associated antigens (TAAs) and MHC Class I and Class II molecules on tumor cells, 3) induction of immunogenic cell death via activation and cross-presentation of tumor antigens by antigen presenting cells (APCs), 4) enhanced function of T effector cells, and 5) decreased function of immunosuppressive cell subsets including Tregs and MDSCs. In addition, HDAC inhibitors are associated with anticancer effects through inhibiting cell cycle progression and inducing apoptosis in tumor cells.

Mocetinostat is an orally administered spectrum-selective Class I/IV HDAC inhibitor specifically targeting HDACs 1, 2, 3 and 11. Given these pleiotropic immune activating effects of class I HDAC inhibitors, combination therapy of mocetinostat with checkpoint inhibition may result in increased efficacy compared to immunotherapy alone.

Nivolumab is a human immunoglobulin G4 (IgG4) monoclonal antibody that binds to the PD-1 receptor and blocks its interaction with PD-L1 and PD-L2, releasing PD-1 pathway-mediated inhibition of the immune response, including the anti-tumor immune response.

This study will evaluate the clinical activity of nivolumab in combination with 3 separate investigational agents, glesatinib, sitravatinib or mocetinostat. The study will begin with a lead-in dose escalation evaluation in small cohorts of patients administered one of the investigational study treatments in combination with nivolumab. Following identification of the dose level to be used in the Phase 2 evaluation for each investigational study treatment, full enrollment will proceed.

Target Population:

Patients with advanced or metastatic non-squamous NSCLC, who have experienced disease progression on or after prior treatment with a checkpoint inhibitor therapy (CIT) (CIT- experienced) or patients who have experienced disease progression after prior first line platinum-based doublet chemotherapy (CIT- naive).

Number in Trial:

As many as 280 patients.

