Guidelines for adverse event management and associated treatment modifications of each agent are provided in Section 5.1.

The dose escalation phase of the study will employ the modified toxicity probability interval (mTPI) method for dose escalation and reduction decision making.

Statistical Considerations:

This Phase 2 study will use a Predictive Probability Design (Lee-2008) in each treatment arm and strata. In creating the statistical designs, the Type 1 error (α) is constrained to <0.05 and Power (1- β) is constrained to \geq 0.90.

Statistical Design Applied to CIT-Experienced and CIT-Naïve with No/Low PD-L1 Expression

The ORR using nivolumab in the population with advanced nonsquamous NSCLC having prior disease progression on a checkpoint inhibitor or patients with non-squamous NSCLC without prior checkpoint inhibitor therapy with no/low PD-L1 expression is assumed to be 5% (p_0); thus, this rate is considered uninteresting. The target ORR using the investigational agents in combination with nivolumab in this study is 30% (p₁). Stage 1 of enrollment will include a minimum of 9 evaluable patients in each treatment strata. With exactly 9 evaluable patients at Stage 1, if at least 1 patient has an Objective Response, 8 additional evaluable patients will be enrolled in the treatment stratum, for a total sample size of 17 evaluable patients. If at least 3 Objective Responses are observed in a treatment stratum, further investigation may be warranted. If the true ORR is 5% (null hypothesis), the probability of early termination during the study is 0.63; the Type 1 error is equal to 0.0466 and the power is equal to 0.9045.

Statistical Design Applied to CIT-Naïve with High PD-L1 Expression

The ORR using nivolumab in the population with non-squamous NSCLC having high PD-L1 expression is assumed to be 27% (p_0); thus, this rate is considered uninteresting. The target ORR using the investigational agents in combination with nivolumab is 50% (p_1).

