3 STUDY DESIGN

Study MRTX-500 is an open-label, parallel Phase 2 evaluation of nivolumab in combination with 3 investigational agents, glesatinib, sitravatinib or mocetinostat, in patients with locally advanced, unresectable or metastatic non-squamous NSCLC. Patients who have experienced progression of disease on or after treatment with a checkpoint inhibitor (CIT- experienced) as well as those who have experienced disease progression after platinum-based doublet chemotherapy (CIT- naïve) will be enrolled. The primary objective is to evaluate the clinical activity of the combination study treatments using ORR in accordance with RECIST 1.1.

Secondary objectives include evaluation of safety, secondary efficacy endpoints, and PK for the investigational agents. The Schedule of Assessments to be performed in the study is presented in Table 1. Pharmacokinetic and blood biomarker sample collection and triplicate ECG assessment time points are presented in Table 2, Table 3, and Table 4. Specifics of two sitravatinib sub-studies are presented in appendices, including the PK evaluation of three sitravatinib capsule formulations (Appendix 5) and, the PK of sitravatinib administered with food (Appendix 6).

The treatment arms included in this study are the following:

- 1. Glesatinib plus nivolumab.
- 2. Sitravatinib plus nivolumab.
- 3. Mocetinostat plus nivolumab.

To control bias in assignment of individual patients to treatment arms and to mitigate the risk of medication errors with the 3 investigational study treatments administered in specific regimens, study sites will be aligned with one specified treatment combination. Site alignment may change as patient cohorts are filled or patient recruitment factors shift at sites.

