4.1 Inclusion Criteria

Patients must meet all of the following inclusion criteria as applicable for phase of the study to be eligible for enrollment into the study:

- 1. Histologically confirmed non-squamous NSCLC with metastatic or unresectable, locally advanced disease, not amenable to treatment with curative intent.
- 2. Receipt of at least one prior treatment in the advanced disease setting.
 - a) CIT-experienced: Most recent treatment must have included a checkpoint inhibitor (i.e., anti-PD-1 or anti-PD-L1 including nivolumab, pembrolizumab, durvalumab, atezolizumab or avelumab) with the result of progression of disease on or after treatment.

Note: For the PK sub-studies as outlined within Appendix 5 and Appendix 6, treatment with a checkpoint inhibitor (i.e., anti-PD-1 or anti-PD-L1) does not need to be included in the most recent treatment.

- b) CIT-naïve: Receipt of prior platinum-based doublet chemotherapy.
- 3. CIT-naïve: Molecular analysis of tumor sample collected following most recent therapy, assessed using the PD-L1 (28-8) CDx assay. Inclusion in the treatment arm will be based on documented no/low PD-L1 expression (positivity < 5% of tumor cells) or high PD-L1 expression (positivity ≥ 5% of tumor cells). *Note: This criterion does not apply to the PK sub-studies as outlined within Appendix 5 and Appendix 6.*
- 4. Measurable disease as per RECIST version 1.1.
- 5. Eastern Cooperative Oncology Group (ECOG) performance status 0, 1 or 2 (Appendix 1).
- 6. Adequate bone marrow and organ function demonstrated by:
 - Absolute neutrophil count $\geq 1,000/\text{mm}^3 \ (\geq 1.0 \times 10^9/\text{L})$
 - Platelet count $\ge 50 \times 10^9 / L \ (> 50,000 \text{ per mm}^3)$

- Alanine aminotransferase (ALT) and aspartate aminotransferase (AST)
 ≤ 2.5 × Upper Limit of Normal (ULN), or ≤ 5.0 × ULN for patients with documented liver metastases.
- Serum bilirubin $\leq 1.5 \times \text{ULN}$ or $\leq 3.0 \times \text{ULN}$ for patients with Gilbert Syndrome or documented liver metastases.
- Serum creatinine $\leq 1.5 \times ULN$.
- 7. \geq 18 years of age.
- 8. Women of child-bearing potential (WOCBP) or men whose partner is a WOCBP agrees to use contraception while participating in this study, and for a period of 6 months following termination of study treatment.
- 9. Completed informed consent process, including signing IRB/EC-approved informed consent form.
- 10. Willing to comply with clinical trial instructions and requirements.

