4.2 Exclusion Criteria

Patients presenting with any of the following will not be included in the study:

- 1. Active brain metastases. Patients are eligible if brain metastases are adequately treated and patients are neurologically stable (except for residual signs or symptoms related to the central nervous system (CNS) treatment) for at least 2 weeks prior to enrollment without the use of corticosteroids, or are on a stable or decreasing dose of ≤10 mg daily prednisone (or equivalent).
 - a. Patients with carcinomatous meningitis
- 2. Patients with any history of tumors that test positive for EGFR, ROS1, ALK mutations or ALK fusions or any other well characterized driver mutations (e.g., RET fusion, TRK alterations, BRAF mutations). Note: The following modification to this criterion applies to the PK sub-studies as outlined within Appendix 5 and Appendix 6: Patients with EGFR, ROS1, ALK mutations or ALK fusions are eligible if previously treated with targeted therapy and/or treatment with a targeted therapy is not indicated.
- 3. Prior therapies: (Note: This exclusion criterion does not apply to the PK sub-studies as outlined within Appendix 5 and Appendix 6)
 - a) Immunotherapies not previously specified, including anti-CTLA-4, anti-OX40 and anti-CD137.

- b) Combination therapy with a checkpoint inhibitor and cancer therapy having the same mechanism of action as the investigational agent intended for use in this study (e.g., tyrosine kinase target or HDAC inhibitor, except prior use of valproic acid for seizures).
- 4. Unacceptable toxicity on prior checkpoint inhibitor treatment (CIT- experienced patients only):
 - a. \geq Grade 3 immune-related AE related to checkpoint inhibitor.
 - b. Grade 2 immune-related AE associated with checkpoint inhibitor unless the AE resolved or was well controlled by withholding the checkpoint inhibitor and/or treatment with steroids, with the exception of prior colitis, myocarditis, and pneumonitis, which are exclusionary.
 - c. CNS or ocular AE of any grade related to checkpoint inhibitor.

NOTE: Patients with a prior endocrine AE are permitted to enroll if they are stably maintained on appropriate replacement therapy and are asymptomatic.

- 5. Active or prior documented autoimmune disease:
 - a. Inflammatory bowel disease (e.g., Crohn's disease, ulcerative colitis).

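### Criterion 2b for CIT-naïve patients asks only for receipt of a platinum doublet, while the target population and design text require progression after it

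*Protocol*

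**What the plan says.** The Study Summary gives the CIT-naïve target population as "patients who have experienced disease progression after prior first line platinum-based doublet chemotherapy". Protocol Section 3 describes enrolment of CIT-experienced patients "as well as those who have experienced disease progression after platinum-based doublet chemotherapy". The design paragraph of the Study Summary and SAP Section 6.0 agree with Section 3. Only the target-population statement specifies first-line treatment.

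The list that decides entry is Protocol 4.1. Parent criterion 2 reads "Receipt of at least one prior treatment in the advanced disease setting". Criterion 2a, for CIT-experienced patients, adds "with the result of progression of disease on or after treatment". Criterion 2b reads "CIT-naïve: Receipt of prior platinum-based doublet chemotherapy" and contains no progression condition.

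In Protocol 4.2, exclusion 3 on prior therapies lists "Immunotherapies not previously specified, including anti-CTLA-4, anti-OX40 and anti-CD137" and certain checkpoint-inhibitor combinations. Neither it nor any other exclusion sets a minimum interval from prior chemotherapy.

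The CIT-naïve cohorts are judged on ORR against fixed null rates of 5% (no/low PD-L1) and 27% (high PD-L1), in Protocol 9.1.2 and SAP 11.1.6.1.

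**The concern.** The list that sites apply is wider than the population the design describes. Progression is required in 2a and missing from 2b, so the omission is specific to CIT-naïve patients.

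The cohorts have no control arm. SAP 8.2.1 counts any confirmed CR or PR, with no rule on attribution. A patient whose tumour is still shrinking after recent chemotherapy could be scored as a study responder. A patient with stable disease after platinum could contribute a longer PFS, which runs from first dose (SAP 8.2.4). Either result could be read as activity of the combination, and responses count towards the go rule.

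The planned checks would not show it. A non-progressed patient who meets 2b as written is not an exception to the eligibility list, so need not appear in the listings of SAP 11.1.2. SAP 11.1.3 summarises the platinum agent received and the best response to a prior checkpoint inhibitor, but neither response to platinum nor progression on it.

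**Working it through.** **Does anything else in the criteria restore progression?**

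- Parent criterion 2 requires prior treatment for advanced disease, not progression on it.
- Criterion 3 (with Protocol 7.3.5 and Table 1, footnote 2) requires a tumour sample taken after the most recent systemic regimen was completed. A patient in partial response can supply one.
- Criterion 4 requires measurable disease, which a partial responder can have.
- The exclusions contain no washout from chemotherapy.
- The baseline scan may be up to 28 days before first dose (Table 1, footnote 13; a 29-day window in SAP 8.2). Nothing requires it to follow the last chemotherapy dose.

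So a patient who completed a platinum doublet without progression and was then biopsied satisfies the list.

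**The plan's own figures.** Let n1 and r1 be the Stage 1 size and threshold, and n and r the final ones. For a true response rate p:

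P(go) = Σ over x ≥ r1 of Bin(x; n1, p) × P(Y ≥ r − x), with Y ~ Bin(n − n1, p).

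- No/low PD-L1 (at least 1/9, then at least 3/17), p = 0.05: 0.2985 × 0.0572 + 0.0629 × 0.3366 + 0.0084 = 0.0466. At p = 0.30 the result is 0.9045. Both match.
- High PD-L1 (at least 5/17, then at least 18/44): 0.0303 at p = 0.27 and 0.9018 at p = 0.50. Both match.

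**Illustration.** Two inputs are assumed and appear nowhere in the documents: f, the share of the cohort entering without progression, and c, the carry-over response rate among them. They can be combined in two ways:

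- Mixture: p = (1 − f)·p0 + f·c. Non-progressed patients respond at rate c instead of p0.
- Additive: p = p0 + f·c·(1 − p0). Carry-over adds responders among those who would not otherwise respond.

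With f = 0.10:

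| c | No/low, mixture: p → P(go) | No/low, additive: p → P(go) | High, mixture: p → P(go) | High, additive: p → P(go) |
|---|---|---|---|---|
| 0.10 | 0.0550 → 0.059 | 0.0595 → 0.071 | 0.2530 → 0.016 | 0.2773 → 0.039 |
| 0.20 | 0.0650 → 0.088 | 0.0690 → 0.101 | 0.2630 → 0.0235 | 0.2846 → 0.049 |
| 0.30 | 0.0750 → 0.122 | 0.0785 → 0.135 | 0.2730 → 0.034 | 0.2919 → 0.062 |

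In the no/low design, the plan's limit of 0.05 is passed in every cell. In the high design it is passed only in the additive form at c = 0.30. In the mixture form the high-design probability falls below 0.0303 whenever c is below 0.27.

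At f = 0.30 and c = 0.30 the no/low figure is 0.34 (mixture) or 0.39 (additive), and the high figure 0.041 or 0.18. These show how strongly the answer depends on the assumptions; they are not estimates.

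**The case against.** The strongest reply is that the intent is clear. Four places state progression. Appendices 5 and 6, in describing sub-study patients who meet the applicable main-study criteria, also name progression after at least one prior treatment. Sites may well have applied it. This stands as far as it goes: the documents do not show that any non-progressed patient entered. It does not remove the contradiction, because Protocol 4.1 is the list that governs entry.

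Several stronger readings are tempting but not supported:

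- *Patients still on maintenance qualify.* The requirement for tissue after completion of the last regimen largely rules them out. The biopsy, and the 14-day PD-L1 turnaround in Protocol 4.4, also tend to put time between chemotherapy and entry. That interval is not guaranteed, since Table 1 asks only that testing begin before study entry.
- *2b ignores disease setting.* Parent criterion 2 already requires treatment in the advanced setting.
- *All the design text says first-line.* Only the target-population statement does, so writing it into 2b would be a choice, not a neutral alignment.
- *The nulls are stated for progressed patients.* For CIT-naïve patients the null statements mention only absence of prior checkpoint therapy and PD-L1 level, as in "prior checkpoint inhibitor therapy with no/low PD-L1 expression is assumed to be 5" per cent. The link to progression is an inference.
- *Shrinkage on chemotherapy counts as response.* Shrinkage achieved before the study baseline is absorbed in it. Only a further confirmed decrease of at least 30% makes a PR (Protocol Appendix 4).

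The consequences are also bounded. Expansion of the CIT-naïve cohorts beyond Stage 2 is not anticipated. Meeting the go rule means only that further investigation may be warranted. The SAP's one-sided 0.025 test is stricter: 3/17 gives p = 0.0503 against 5%, so 4/17 (p = 0.0088) is needed.

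**Conclusion.** The contradiction is real and should be corrected. The eligibility list admits patients outside the stated CIT-naïve population, and nothing else in the criteria closes that gap. The stated sample sizes, Type 1 error and power are arithmetically right; the question is whether the null rates apply to everyone 2b admits.

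The size of any bias cannot be derived from the documents. With an assumed 10% of non-progressed patients and a 10–30% carry-over rate among them, the no/low PD-L1 false-go probability is about 0.06–0.13 instead of 0.0466. On the same assumptions the high PD-L1 figure is 0.016–0.062 against 0.0303. A reader might infer that the CIT-naïve ORR is in fact inflated; the documents do not support that.

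The point is confined to the CIT-naïve strata. In practice that means sitravatinib, because SAP 4.1.1 and 4.1.2 limit glesatinib reporting to the lead-in and record that mocetinostat enrolment never began. The CIT-experienced cohort of up to 125 patients is covered by 2a.

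**What to change.** **Protocol.** Reconcile 2b with the Study Summary, Section 3 and SAP 6.0, so that progression on or after platinum-based doublet chemotherapy is an explicit entry requirement. The sponsor should also decide whether the doublet must be first-line and make the target-population statement and the other sections agree.

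**SAP.** Add a sensitivity CIT-naïve ORR and go-rule count, by PD-L1 stratum. Exclude patients without documented progression before first dose, and those whose baseline scan precedes the last dose of prior therapy.

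**Cost.** One line of eligibility text and one additional table. No sample size or threshold changes, and 0.0466 and 0.0303 remain the design figures. The SAP foresees a final version before database lock (Section 4.0), so the addition can go there. One limit remains: Table 1 shows that disease history and prior therapy are collected, but not whether progression on platinum is dated. The analysis should be done as far as those data allow, and the number of patients who cannot be classified should be reported.

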4.2 Exclusion Criteria

Patients presenting with any of the following will not be included in the study:

- 1. Active brain metastases. Patients are eligible if brain metastases are adequately treated and patients are neurologically stable (except for residual signs or symptoms related to the central nervous system (CNS) treatment) for at least 2 weeks prior to enrollment without the use of corticosteroids, or are on a stable or decreasing dose of ≤10 mg daily prednisone (or equivalent).
 - a. Patients with carcinomatous meningitis
- 2. Patients with any history of tumors that test positive for EGFR, ROS1, ALK mutations or ALK fusions or any other well characterized driver mutations (e.g., RET fusion, TRK alterations, BRAF mutations). Note: The following modification to this criterion applies to the PK sub-studies as outlined within Appendix 5 and Appendix 6: Patients with EGFR, ROS1, ALK mutations or ALK fusions are eligible if previously treated with targeted therapy and/or treatment with a targeted therapy is not indicated.
- 3. Prior therapies: (Note: This exclusion criterion does not apply to the PK sub-studies as outlined within Appendix 5 and Appendix 6)
 - a) Immunotherapies not previously specified, including anti-CTLA-4, anti-OX40 and anti-CD137.

- b) Combination therapy with a checkpoint inhibitor and cancer therapy having the same mechanism of action as the investigational agent intended for use in this study (e.g., tyrosine kinase target or HDAC inhibitor, except prior use of valproic acid for seizures).
- 4. Unacceptable toxicity on prior checkpoint inhibitor treatment (CIT- experienced patients only):
 - a. \geq Grade 3 immune-related AE related to checkpoint inhibitor.
 - b. Grade 2 immune-related AE associated with checkpoint inhibitor unless the AE resolved or was well controlled by withholding the checkpoint inhibitor and/or treatment with steroids, with the exception of prior colitis, myocarditis, and pneumonitis, which are exclusionary.
 - c. CNS or ocular AE of any grade related to checkpoint inhibitor.

NOTE: Patients with a prior endocrine AE are permitted to enroll if they are stably maintained on appropriate replacement therapy and are asymptomatic.

- 5. Active or prior documented autoimmune disease:
 - a. Inflammatory bowel disease (e.g., Crohn's disease, ulcerative colitis).
 - b. History of interstitial lung disease (ILD), drug-induced ILD, radiation pneumonitis which required steroid treatment, or any evidence of clinically active interstitial lung disease.
 - c. Active or prior documented autoimmune disease within the past 2 years. NOTE: Patients with Type I diabetes, vitiligo, Grave's disease, or psoriasis not requiring systemic treatment (within the past 2 years) are not excluded.
- 6. Active or prior immunocompromising conditions:
 - a. Current or prior use of immunosuppressive medication within 28 days before the first dose of study treatment, with the exceptions of topical, ocular, intranasal and inhaled corticosteroids (with minimal absorption) or systemic corticosteroids at physiological doses, which are not to exceed 10 mg/day of prednisone, or an equivalent corticosteroid. A brief course (≤ 3 days) of systemic corticosteroids >10 mg/day of prednisone (or equivalent corticosteroid) for prophylaxis (e.g., contrast dye allergy) or for treatment of non-immune conditions (e.g., delayed-type hypersensitivity reaction caused by a contact allergen) is permitted within the 28 days.
 - b. Known acute or chronic human immunodeficiency virus (HIV).

- c. History of primary immunodeficiency.
- d. History of allogeneic transplant.
- 7. Known acute or chronic hepatitis B or hepatitis C. Patients treated for hepatitis C with no detectable viral load are permitted.
- 8. History of hypersensitivity to study treatment excipient.
- 9. History of stroke or transient ischemic attack within the previous 6 months.
- 10. Any of the following cardiac abnormalities:
 - a. Unstable angina pectoris.
 - b. Congestive heart failure \geq NYHA Class 3.
 - c. QTc >480 milliseconds.
 - d. Sitravatinib and mocetinostat treatment arms:
 - i. LVEF <40% (sitravatinib and mocetinostat only).
 - ii. Current or history of a small, moderate or large pericardial effusion, and/or hemodynamic compromise due to pericardial effusion of any size. Minimal or trivial pericardial effusion is not excluded (mocetinostat only).
- 11. Concomitant medication known to cause prolonged QT which cannot be discontinued or changed to a different medication prior to enrollment (Appendix 3).
- 12. Known or suspected presence of another malignancy that could be mistaken for the malignancy under study during disease assessments.
- 13. Pregnancy. WOCBP must have a negative serum or urine pregnancy test documented within the screening period prior start of study drug.
- 14. Breast-feeding or planning to breast feed during the study or within 6 months after study treatment.
- 15. Any serious illness, uncontrolled inter-current illness, psychiatric illness, active or uncontrolled infection, or other medical history, including laboratory results, which, in the Investigator's opinion, would be likely to interfere with the patient's participation in the study, or with the interpretation of the results.

